## Specific Aim #2: To determine whether adjunctive ketamine is associated with opiate sparing.

This will be measured by documenting each participant's number of Requests for Additional Analgesic Medications (i.e., RAAMs) for acute nociceptive pain during each of the 14 wound care procedures from Day 1 to Day 7 of the Trial.

**The seven secondary outcome measures** of the proposal are: 1) Rates of acute and posttraumatic stress disorder (i.e., ASD and PTSD); 2) Rates of major depressive disorder; 3) Sleep quality and duration; 4) Pain-related anxiety; 5) Catastrophizing; 6) Emotion Regulation and; 7) Trauma resilience.

1) ASD and PTSD will be assessed using the Diagnostic and Statistical Manual of Mental Disorders V-(DSM V). By definition, to meet criteria for PTSD, symptoms must be present for 1 month. As such, prior to the 1-month post-injury time-point, subjects with symptoms consistent with PTSD related to their burn injury will be diagnosed with ASD, rather than PTSD. It is hypothesized that subjects in the K + UC group will have a lower percentage of patients who meet criteria for PTSD, when compared to subjects in the UC group. It is also hypothesized that a number of factors will moderate the presence and severity of ASD and PTSD; these include:

a) Pain, as measured above. Mutual Maintenance Theory: We anticipate that "mean pain" of all 14 sessions (i.e., group average of all observations across all 14 sessions) and the trajectory of pain through the 14 sessions (i.e., group X individual trajectory within session, and, group X individual trajectory across all 14 sessions) will be predictive of PTSD development and PTSD symptom severity at 1-month.

b) Sympathetic reactivity (as measured above). We expect that greater sympathetic reactivity during the wound care procedures will be associated with ASD and PTSD.

c) Depressive symptom severity as measured using the Beck Depression Inventory (BDI-II) during the week of wound care, and at the 1-month time-point.

d) Sleep during the night following wound procedures (measured by both self-report and with the Itamar Watch-PAT200) and at the 1-month time point (self-report).

e) Trauma Resilience (as measured using the Trauma Resilience Scale: Trait- at baseline, and at 1-month time-point).

f) Distress at baseline in reporting the burn event (as measured by self-report and the Itamar Watch-PAT200)

g) Optimism (as measured by the Life Orientation Test: Trait – baseline)

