h) Emotion Regulation (as measured by the Emotion Regulation Scale-State: baseline and post-procedure)

**2) Major Depressive Disorder**: It is hypothesized that subjects in the K + UC group will have significantly lower rates of major depressive disorder, as defined by the DSM V and Beck Depression Inventory-II, than subjects in the UC condition. It is anticipated that the same factors that are hypothesized to moderate ASD and PTSD (see above) will moderate major depressive disorder. Further, we anticipate that severity of ASD and PTSD will be predictive of severity of major depressive disorder.

**3) Sleep:** Sleep will be assessed by the Itamar Watch-PAT 200, and by self-report (Insomnia Severity Index, and, Sleep-Pain Diary). It is hypothesized that subjects in the K+UC group will have superior sleep to those in the UC group. The same factors that are hypothesized to moderate PTSD and depression are anticipated to moderate sleep quality.

**4) Pain Anxiety Symptom Scale-20** (Kleiman, 2011) will be used to test the hypothesis that the K+UC condition, when compared to the UC condition will result in significantly fewer symptoms of pain-related anxiety at 1-month follow-up. Similarly, these measures will be used to test the hypothesis that pain anxiety assessed within 1 hour prior to start of Sessions 1, 5 and 7 will moderate the effect of Study Drug on measures of acute pain. Finally, this measure will be used to test the hypothesis that change in pain anxiety will moderate the effect of study drug on change in PTSD symptoms and PTSD diagnosis.

**5) Catastrophizing:** Pain-related catastrophizing will be measured using the Pain Catastrophizing Scale (PCS; Sullivan, 1995) which was developed to assess three components of catastrophizing: rumination, magnification, and helplessness. It is hypothesized that the K+UC condition, when compared to the UC condition will result in significantly fewer symptoms of pain-related catastrophizing at 1-month follow-up. It is also hypothesized that pain-related catastrophizing assessed within 1 hour prior to start of Day 1 (Session 1), Day 4 (Session 7) and Day 7 (Session 13) will moderate the effect of Study Drug on measures of acute pain (across all 7 days and 14 sessions, as well as during Sessions 1, 7 and 13 respectively).

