REFERENCES Reference Details in: Liu, Lin, Wu, Zhou, 2016 Anticevic et al., 2012 Chan et al., 2013 Curran, Morgan, 2000 Honey et al., 2005 Honey et al., 2004 Liang et al., 2013 Morgan et al., 2010 Price et al., 2014 Solé et al., 2015 Stone et al., 2015

Evidence for ketamine effect in reducing behavioral and physiological aspects of anxiety and depression.

Recently, ketamine has also been shown to hold promise as a cutting edge therapy for chronic, treatment-resistant major depression (Lapidus, 2014) and chronic posttraumatic stress disorder (PTSD; Feder, 2014).

There is a rapidly expanding interest in pharmaceutical interventions alone or in combination with prolonged exposure that may, in the face of acute trauma exposure, facilitate the prevention, resilience or early recovery from symptoms of PTSD and stress-related depression symptoms (Weng, et al, 2013). Although these are not primary outcome measures in the proposed Ketamine for Acute Pain in Burns study, many patients with significant burn injuries develop PTSD and/or depression, in part related to the wound cleansing/debridement process. As such, in addition to evaluating the utility of ketamine as an adjunct to opiates for the purposes of pain management, the current proposal will evaluate its potential effects on psychological and psychiatric outcomes (i.e., stress, mood, PTSD, depression, sleep).

Engin, et al., (2009) note that demonstrating ketamine's effects on depression and anxiety are complicated in human trials because of its' dissociative anesthetic properties "which are obvious to both patients and clinicians" as well as in animal models that are often confounded by "ketamine's side-effects on general activity, which have not been routinely measured or taken into account in experimental studies" (p. 359).

They report on a rigorously designed set of animal experiments wherein ketamine decreased "behavioral despair in the forced swim test, a widely used rat model of antidepressant drug action." This effect was not confounded by side-effects on general activity, and was comparable to that of a standard antidepressant drug, fluoxetine."

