2) *Opiate Sparing*: ketamine alone, relative to fentanyl alone, required less additional pain medications, on average, when the ketamine dose was 0.3 mg/kg but not when it was 0.15 mg/kg;

3) *Serious Side Effects*: Relative to placebo and to fentanyl groups, ketamine participants were at significantly greater risk for neurological and psychological side effects and minor cardiopulmonary events. In contrast, participants in both the fentanyl group and placebo group who received additional opioids were at greater risk of major cardiopulmonary events. No major cardiopulmonary events were observed in the ketamine group.

Also recently, Wang (2016) conducted a systematic review and meta-analysis of 22 RCTs evaluating the safety and efficacy of ketamine, adjunctive to opiates, in managing post-operative pain, opiate sparing, and reduction in opiate side effects (Wang, Johnston, et al., 2016). The post-operative setting is not closely analogous to the wound care model for severe acute pain in austere conditions which is applied in our design. However, post-operative pain has applications in burn injuries such as with donor site pain that is observed following skin grafting for wound closure. Post-operative pain control also appears to be the most active area of ketamine-research related to pain. Wang et al report that compared to PCA morphine augmented with hydromorphone, the ketamine augmentation resulted in an average reduction in pain of < 1.0 cm on a 10.0 cm visual analog scale (VAS), and, more impressively, reduced cumulative morphine consumption across post-operative days 1-3 (range = 5-20 mg). In the few studies reporting side effects, nausea and vomiting were reduced in the ketamine adjunct groups.

**Evidence Update for Secondary Aims:** Low-dose, slow infusion ketamine as an adjunct to fentanyl, when compared to slow infusion saline placebo as an adjunct to fentanyl reduce Symptoms of Acute Stress Disorder and provide Evidence of PTSD Prevention Effect.

Evidence from the empirical literature indicates that the Secondary Aims of the Ketamine RCT study will address important objectives with relevance to military operations and personnel.

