This brief review presents evidence that acute pain and symptoms of PTSD have been shown to be highly comorbid in many trauma-exposed populations including combat veterans. This first article investigated the hypothesis that combat-exposed veterans with PTSD have distinct responses to painful stimuli indicative of central sensitization. Central sensitization is "plasticity of the somatosensory system" and has been defined as "a heightened response of neurons and circuits in nociceptive pathways as a result of increased excitability and synaptic efficacy or reduced inhibitory modulation" (REFS 31-33). Experimentally induced pain (capsaicin injection) was administered on 2 separate days, as were thermal and mechanical sensitivity stimuli (Quantitative Sensory Testing) in subjects with combat-related PTSD and combat-exposed controls without PTSD (Moeller-Bertram, Strigo, et al., 2016). After the second day of experimental pain, the group with PTSD, relative to the combat control group, showed:

1) Temporal Summation: significantly slower decay over time in mean pain severity ratings (0-10 VAS) and mean pain unpleasantness ratings (0-10 VAS), and,

2) Hyperalgesia: significant "increase in pain intensity rating following repeated application of pressure stimuli..." (P. 767).

This pattern of findings provides evidence for a greater degree of central sensitization to pain among combat veterans with PTSD relative to combat veterans without PTSD. Indeed, Central Sensitization can manifest as pain hypersensitivity (hyperalgesia) and enhanced temporal summation [31,59–62].

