# **Exclusion Criteria:**

- Requiring endotracheal intubation and sedation
- Diminished Level of Consciousness / Cognitive Function:  $MMSE \leq 20$ .
- Diminished Capacity Incapable of providing informed consent (reason(s) to be listed).
- PMH: Insensate to pain in burn wound location (e.g., SCI; peripheral neuropathy)
- Safety: Contra-indication (e.g., potential drug interactions, medical comorbidities)
- 1. Protocol: Study Design, Dosing & Duration:
  - a. Design: Triple blind (nurse, patient, RA) Randomized Controlled, parallel group Trial (RCT):

Group 1: Usual Care plus Saline placebo (IV Fentanyl plus Saline slow infusion administered via programmed pump)

Group 2: Usual Care plus Ketamine augmentation (IV Fentanyl plus low-dose Ketamine slow infusion administered via programmed pump)

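### Without a pre-burn history of PTSD and major depression, the 1-month rates cannot be read as prevention, and a causal reading of the pain-PTSD link is open to confounding

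*Combined protocol and SAP*

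**What the plan says.** **Incidence wording.** Section 3 (Background, Evidence Update for Secondary Aims) speaks of "Evidence of PTSD Prevention Effect". Section 2, secondary outcome 1(a), says under a mutual maintenance theory that mean pain and its trajectory "will be predictive of PTSD development and PTSD symptom severity at 1-month".

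**Hypotheses compared between arms.** For PTSD the ketamine arm is expected to have "a lower percentage of patients who meet criteria for PTSD, when compared to subjects in the UC group". For depression, "subjects in the K + UC group will have significantly lower rates of major depressive disorder". Neither is limited to new cases.

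**Tie to the burn.** Before 1 month, "subjects with symptoms consistent with PTSD related to their burn injury will be diagnosed with ASD, rather than PTSD". There is no matching rule for major depression, and none for a 1-month PTSD diagnosis in someone who already had PTSD.

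**Entry criteria.** The only past-history exclusion is insensitivity to pain at the wound. The nearest general clause is "Safety: Contra-indication (e.g., potential drug interactions, medical comorbidities", which names neither disorder.

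**Baseline.** Section 4, after the Randomization paragraph, has severity of acute stress, depression, anxiety and insomnia symptoms assessed at enrolment before the first target dressing change. These are checked for balance, related to core outcomes, and allowed for if necessary. The Data Analysis Plan adds covariates that are unbalanced between arms, or non-study factors substantially associated with pain intensity.

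**The concern.** The plan's own background makes two alternative explanations plausible.

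1. It reports that "ketamine has also been shown to hold promise as a cutting edge therapy for chronic, treatment-resistant major depression", and says the same of chronic PTSD. A lower 1-month rate could then come from relieving disorder that was present before the burn, with no new case averted.

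2. Its review of an experimental pain study says that the pattern "provides evidence for a greater degree of central sensitization to pain among combat veterans with PTSD relative to combat veterans without PTSD", and the next paragraphs liken burn pain to that experimental model. Pre-burn PTSD could therefore raise both in-hospital pain and PTSD at 1 month. Randomization does not protect this analysis, because pain is not randomized. A rule that adds covariates when the arms are unbalanced does not address a confounder that acts within the whole cohort, and a history nobody recorded cannot be added to a model later.

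At stake is what the secondary results may be said to show: prevention, and pain as a contributor to PTSD. The primary pain and opiate-sparing aims are not affected.

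**Working it through.** **1. Reproduce the plan's figures (Sample Size sections).** Inputs: difference 2.0 NAS points, alpha 0.05 (two-sided reproduces), power 80%, ICC 0.7. Design effect DE = 1 + (m − 1) × ICC; n per arm = unclustered n × DE / m.

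- SD 3, m = 14: DE = 1 + 13 × 0.7 = 10.1; 37 × 10.1/14 = 26.7, so 27.
- SD 4, m = 11: DE = 1 + 10 × 0.7 = 8.0; 64 × 8/11 = 46.5, so 47.

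Both match. The same inputs imply the SD of a patient's mean pain: √(9 × 10.1/14) = 2.55 and √(16 × 8/11) = 3.41. The documents give no figure for PTSD, depression or pre-burn prevalence, so **every rate below is an assumption**.

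**2. Can a lower rate appear with no prevention?** 1-month rate = prevalence × persistence + (1 − prevalence) × new onset. Assume new onset 15% in both arms and persistence 80% (usual care) v 50% (ketamine).

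| Pre-burn prevalence | Usual care | Ketamine |
|---|---|---|
| 10% | 0.08 + 0.135 = 21.5% | 0.05 + 0.135 = 18.5% |
| 20% | 0.16 + 0.12 = 28.0% | 0.10 + 0.12 = 22.0% |
| 30% | 0.24 + 0.105 = 34.5% | 0.15 + 0.105 = 25.5% |

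The gap of 3 to 9 points is entirely persistence. With 80% persistence and new onset of 15-30%, old cases would be 12-22% of all 1-month cases at 5% prevalence and 53-70% at 30%. For PTSD this applies only so far as old PTSD is counted at 1 month.

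**3. Could an imbalance arise unseen?** At 47 per arm the 95% range for a chance difference in prior disorder is ±1.96 × √(2q(1 − q)/47): ±9, 12, 16 and 19 points at q = 5, 10, 20 and 30%. It could not be checked without the history.

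**4. Pain-PTSD association with no causal effect of pain.** Simulation: N = 94; prior PTSD shifts mean pain by d points; 1-month PTSD is 80% with and 20% without prior PTSD; two-sample t test of mean pain by 1-month PTSD. Counted: p < 0.05 in the direction of more pain (nominal 2.5%). Ranges cover SD 3.41 to 2.55.

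| Prevalence | d = 0.5 | d = 1 | d = 2 |
|---|---|---|---|
| 5% | 3-4% | 4% | 6-8% |
| 10% | 4-5% | 5-7% | 11-15% |
| 20% | 5-6% | 8-11% | 20-33% |
| 30% | 5-7% | 11-16% | 28-46% |

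If 1-month PTSD is 50% v 20% instead, with d = 1, the figure is about 4-8% at 10-30% prevalence. As an odds ratio, confounding alone gives 1.07-1.14 at 5% prevalence and 1.24-1.55 at 30% (high pain in 60-70% with prior disorder v 50% without; PTSD 80% v 20%).

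**5. What repairs it.** Restricting to patients without prior PTSD returns 2-3%, if history is classified perfectly. Adjusting only for a post-burn severity score helps in part. At 20% prevalence, d = 2 and SD 2.55, about 34% falls to 10-16% if the score separates prior cases by 2-3 SD, but only to 27% at 1 SD.

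**The case against.** **The prevention phrase is a literature heading; the tested hypothesis is a lower percentage.** True, and a reader might infer that the arm comparison itself is invalid. It is not: prior disorder is balanced in expectation, so the rate difference is a sound total effect. Only the label goes beyond it.

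**Baseline psychiatric state is recorded.** A reader might infer that nothing is collected. Section 4 does collect pre-treatment severity, and the objectives add baseline resilience, optimism and distress about the burn. These can partly adjust. They carry no diagnosis or onset date, and are taken after the injury.

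**PTSD is tied to the burn.** This stands for early symptoms, so it is too strong to say that old and new PTSD cannot be told apart. The plan still does not say how a 1-month diagnosis is attributed when PTSD came first.

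**Pain that predicts PTSD is a true prediction, not a false positive.** Correct for the stated risk-stratification purpose (Trajectory, and, Mediator / Moderator Analyses). The error rates above apply only to a causal reading. The mutual maintenance hypothesis and the Background's stated aim of establishing mechanisms invite that reading.

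**The inputs are chosen high.** Fair: a 2-point shift equals the plan's own clinically significant treatment difference, and with small shifts or low prevalence the inflation is slight.

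**The history may be planned elsewhere.** The protocol cites a Manual of Operations and refers to a measures list, neither of which is in the text reviewed. If the items are there, only the analysis and wording changes remain.

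**Conclusion.** The point holds in this form. Pre-burn PTSD and major depression are neither excluded nor, in the protocol and SAP, planned to be recorded as history. The 1-month rate comparison supports a statement about total effect but not one about prevention, most clearly for major depression. Pain may be reported as a predictor of 1-month PTSD, but not as a contributor to it without accounting for prior PTSD.

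The size cannot be fixed from the documents. Under the assumptions shown, the chance of a significant positive association with no causal effect is close to nominal (about 3-8%) at 5% prevalence or a 0.5-point shift. It passes 40% only in the corner with 30% prevalence, a 2-point shift, the smaller SD and 80% v 20% PTSD. The upper figure should not be quoted as the expected error.

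These are secondary outcomes, so this is a worthwhile improvement and not a threat to the primary aims. It is best made before enrolment, because history asked after treatment is more exposed to recall bias.

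**What to change.** 1. Before randomization, record two yes/no items from chart and patient: PTSD before the burn, and major depression before the burn.
2. Keep the all-randomized 1-month rate as the main result, described as a total effect and without prevention wording.
3. Add a supportive analysis of new-onset disorder among patients without that disorder before the burn, and report persistence separately in those with it. State how a 1-month PTSD diagnosis is attributed when PTSD predates the burn.
4. In the models for secondary outcome 1(a), adjust for pre-burn PTSD and the baseline severity scores regardless of balance between arms. Restrict to patients without prior PTSD as a sensitivity analysis.
5. If the history is not collected, drop the prevention wording and present pain as a predictor only.

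**Cost.** Two form items and a few lines of SAP text. The new-onset analysis shrinks from 47 per arm to 42, 37 or 32 at 10, 20 or 30% assumed prevalence (47 × 0.9, 0.8, 0.7, rounded down). Power for an assumed 30% v 15% falls from 41% to 38, 34 or 30%; it was low already, which is why this analysis should be supportive. History taken by recall in acutely burned patients will be misclassified to some degree, so some confounding will remain.

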# 4. Study Procedures a. Study design:

Patients will be recruited through the population of adults 18-70 years of age admitted with acute burn injuries to the Johns Hopkins Burn Center. The consent designees (fellows, attendings) will approach potential study participants, and using methods documented in the study-specific Manual of Operations and approved by the IRB, describe study goals, aims, and methods to insure that potential subjects have the opportunity to make an informed decision, are aware of alternatives to participation, etc... Subjects must meet the following inclusion / exclusion criteria:

# **Inclusion Criteria:**

- Acute burn injury with TBSA  $\geq 2\%$  &  $\leq 40\%$ .
- Adults 18-70 years of age admitted to the JHBC with acute burns
- Estimated length of stay on day of admission  $\sim \geq 5$  and, optimally  $\geq 7$  days.
- Pain rated NAS ≥5 in Emergency Room during initial wound evaluation / debridement or on admission to the BICU / debridement.

# **Exclusion Criteria:**

- Requiring endotracheal intubation and sedation
- Diminished Level of Consciousness / Cognitive Function:  $MMSE \leq 20$ .
- Diminished Capacity Incapable of providing informed consent (reason(s) to be listed).
- PMH: Insensate to pain in burn wound location (e.g., SCI; peripheral neuropathy)
- Safety: Contra-indication (e.g., potential drug interactions, medical comorbidities)
- 1. Protocol: Study Design, Dosing & Duration:
  - a. Design: Triple blind (nurse, patient, RA) Randomized Controlled, parallel group Trial (RCT):

Group 1: Usual Care plus Saline placebo (IV Fentanyl plus Saline slow infusion administered via programmed pump)

Group 2: Usual Care plus Ketamine augmentation (IV Fentanyl plus low-dose Ketamine slow infusion administered via programmed pump)

# STUDY PROTOCOL: Medications, Dose, Delivery Modality, Timing -

The changes in dosing, described below, are made to more concretely specify the dosing in this trial and to provide ketamine in doses similar to that in other studies that have been conducted using ketamine for acute pain. This level of detail had not been included in the original of this irb-approved protocol, rather, a range of doses was specified.

# **STUDY DRUG GROUP** (Fentanyl PLUS Ketamine):

- 1. Ketamine Loading Dose (Study Drug, slow infusion) =
  - 0.3 mg/kg, initiated approximately 10 minutes prior to start of wound care with pump set to deliver slowly over approximately 5 minutes... *THEN*,
- 2. Fentanyl (UC, injection) =
  - 1 mcg / kg. This is given to participants in both Group 1 and Group 2 initiated < 1 minute prior to wound care.
- 3. Ketamine (Study Drug, Infusion) =
  - 2.5 mcg/kg/min, with the pump set to initiate infusion immediately following the Loading Dose and continued for the duration of the session. The EPIC order set specifies that the nurse determines when the session is over, and that the nurse will turn off the infusion at that point.

